UPIRTSO	Unanticipated Problems Involving Risks to Subjects or Others

PROTOCOL SUMMARY

Title:	Dietary Impact on Intestinal Sulfate Metabolism
Phase:	1
Population:	30 healthy male and female volunteers. Subjects will be recruited from the Twin Cities metropolitan area and will participate as outpatients in this study.
Number of Sites:	1 (University of Minnesota)
Study Duration:	12 months
Subject Participation Duration:	Approximately 1 month
Agent or Intervention:	Dietary intervention will consist of following diets high in sulfur-containing amino acids (SAAs) and low in SAAs for 7 days each, with a 14-day washout period between interventions
Objectives:	The primary objectives of this proposal are to: 1) Compare low sulfur and high sulfur diets with respect to fecal production of hydrogen sulfide (H_2S) and other end products of microbial fermentation; and 2) Determine whether the diet alters the fecal microbiota and the relative proportion of fecal sulfate reducing bacteria.
Endpoints:	The primary endpoint is the change in H_2S concentration measured by gas chromatography. Comparisons will be made between the baseline measurement (Day 0) and end of intervention (Day 7) for each diet (within-group comparison) and between high- and low-sulfur diet H_2S concentration on Day 7 (between group comparison).

1 BACKGROUND INFORMATION AND SIGNIFICANCE

Ulcerative colitis (UC) is one of the two major inflammatory bowel disease (IBD) subtypes and is characterized by chronic, relapsing inflammation in the colon causing diarrhea and rectal bleeding. UC currently affects 0.25% of the population in North America (~ 1 million people in the United States), having risen dramatically over recent decades, and is now emerging as a global disease.¹ UC is responsible for significant personal, professional, and economic consequences - annual costs associated with medical management approach \$5 billion.² The causes for flares and remissions in UC activity are largely unknown, although epidemiologic studies suggest a significant role of the environment in the emergence of IBD. Thus, there is rising incidence in Europe and North America,^{3,4} higher incidence in developed countries as compared to non-industrialized countries,^{5,6} and increasing incidence rates in developing countries as they have Westernized.⁷

Patients with UC instinctively understand that diet is an important variable in diseases involving the intestinal tract, and they have a strong interest in dietary modifications that may aid in maintaining remission of symptoms and improving their disease. When first diagnosed, virtually all patients with IBD ask what they should eat to help control their disease. To a large extent, this reasonable and intuitively logical question remains unanswered, as there is a scarcity of well-designed, prospective interventional studies that can guide dietary recommendations for this patient population. Current allopathic therapeutic strategies rely exclusively on drugs and surgery to control intestinal inflammation and deal with its complications. However, these available therapies are commonly not sufficient to control the symptoms, risk serious side effects, and come at a high financial cost. Therefore, patients and doctors alike seek effective complementary therapies.

The intestinal tract contains complex microbial communities that participate in the final steps of the digestive process. The structure and composition of these communities is highly responsive to dietary input.⁸ Some of the end products of microbial metabolism in the gut are highly toxic (e.g., H₂S) and may be linked to the pathogenesis of UC.^{9,10} These potentially toxic compounds can damage the epithelial lining of colon, cause breakdown of the gut barrier, and lead to inflammation. Fecal H₂S concentration is increased by increasing either the sulfur amino acid¹¹ or sulfate content (as additives) of the diet.¹² Sulfur-containing amino acids (SAA) are converted to sulfides by sulfate reducing bacteria (SRB)^{13,14}, which may expand in response to increased availability of SAA and inhibition of alternative end routes of fermentative pathways, e.g., production of methane or short-chain fatty acids (SCFAs).^{15,16}

The scientific foundation for the sulfur-containing toxin hypothesis as a driver of UC rests on provocative and compelling evidence from clinical observations, animal models, and dietary association studies. The characteristic distribution of UC in the colon (always involving the rectum and continuously extending proximally to varying extent of involvement) is suggestive of a toxin being concentrated along the path of intestinal transit. Sulfated dextrans, but not free dextrans, can induce experimental colitis in rodent models.¹⁷ H₂S, a potent toxin in its own right and one of the suspected sulfur-containing toxins in UC, decreases butyrate utilization by colonocytes and causes loss of gut barrier function.^{9,18} UC patients have been found to have increased luminal concentrations of H₂S and disease activity correlates with sulfide production

rates.^{10,19} Furthermore, some medications that have beneficial effects on UC activity, e.g., mesalamine and aminoglycoside antibiotics, can inhibit SRB.^{20,21} The major dietary sources of sulfur are high-protein foods (containing the SAAs methionine and cysteine), cruciferous vegetables from the *Brassicaceae* family, and processed food preservatives.²² Dietary sources of sulfur exceed endogenous sources in the colon,²³ and dietary intake studies have found a greater risk of UC flares in individuals consuming diets with higher sulfur content.^{24,25} When taken together, these mechanisms suggest that minimizing intake of dietary SAAs may improve symptoms and reduce risk for disease exacerbation in individuals with UC.

Diet-derived sulfur is not the only determinant for the availability of sulfur to microbiota in the colon. Saturated fats (mainly animal-derived), as opposed to unsaturated fats (mainly plant-derived) promote taurine conjugation of hepatic bile acids. Taurine provides a source of organic sulfur to SRB such as *Bilophila wadsworthia*, which blooms in mice fed a high-milk fat diet, but not a high-safflower fat diet.²⁶ Furthermore, the high-milk fat diet induces *B. wadsworthia*-specific Th1 cells in the gut-associated lymph nodes and greater incidence of colitis in genetically susceptible (IL-10-/-) mice. Different bile acids themselves can have potent effects on microbiota, both inhibitory and stimulatory, on different members of microbiota. *B. wadsworthia* is clearly favored by taurocholate, and this is also true of *Clostridium difficile*, which is a common trigger for flares of UC activity.^{27,28}

The notion of a “low sulfur diet” for treatment of gastrointestinal conditions has existed for decades. Restricting high-sulfur foods, in combination with milk fat restriction, has historically been recommended to UC patients by some practitioners of integrative medicine. However, and despite these claims, the methodology of this diet was ill-defined and it is not known whether it results in specific changes in gut microbiota, decreases production of toxic sulfur-containing end products, or is even feasible in terms of adherence. The medical literature contains only a single small clinical case series of 4 patients with UC from approximately 20 years ago that demonstrated symptomatic improvement on a low sulfur diet that restricted meat, milk fat, cruciferous vegetables, and inorganic sulfates used as food preservatives.²⁹ This work did not include objective measurements of disease activity, such as laboratory or endoscopic criteria, which would be standard today. One prospective cohort study²⁴ published in 2004 measured dietary intake via food frequency questionnaire and found that a high intake of meat and meat products (particularly red and processed meats), eggs, protein, alcohol, energy, fat, sulfur, and sulfate (a common food and beverage additive) predicted an increased likelihood of relapse. However, data on sulfur content of foods was only listed for 29% of foods consumed by participants in the study, indicating incompleteness of the full total of sulfur intake. Notably, sulfur content was not available for red and processed meats, which are known to be high in dietary sulfur. Therefore, more complete food tables for sulfur would be expected to increase the differences in sulfur consumption between participants who did or did not relapse.

The scarcity of rigorous, systematic investigations of dietary interventions in UC patients is a consequence of several factors: (1) controlling diet in human subjects is difficult, (2) dietary input is complex, and (3) clinical end points alone provide few opportunities for mechanistic dissections. However, the rise of high throughput DNA sequencing and metabolomics, combined with novel computational techniques over the past decade, is opening an entirely new era in

nutrition research. The gut microbiota, unlike human individuals, can serve as very accurate reporters of environmental changes.

The long-term goal of our research group is to develop evidence-based nutritional strategies for UC that compliment medical therapies. Our strategy is to link specific diets to their effects on microbiota functionality. Nevertheless, we understand that even when armed with the new powerful tools, identifying an effective diet that is also acceptable to patients will be a challenging and resource intensive journey. Therefore, in this proposal, which is our first step toward that ultimate goal, we will test dietary extremes in highly motivated, healthy volunteers. This will allow us to streamline our experimental toolkit and measure the magnitude of the potential effects on gut microbiota composition and function that can be achieved by controlling the diet, which will help to estimate the size of a formal clinical study in patients with UC.

2 STUDY HYPOTHESES AND OBJECTIVES

2.1 Hypotheses

Our hypotheses are that excessive production of toxic sulfur-containing end products of microbial fermentation in the colon are major drivers of UC, and that it is possible to decrease their production by dietary means.

2.2 Primary Objectives

The primary objectives of this study are:

1. Compare low sulfur (Low-S) and high sulfur (High-S) diets with respect to fecal production of H₂S and other end products of microbial fermentation, such as thiols, hydrogen gas (H₂), and methane (CH₄) (prediction: higher H₂S with High-S diet).
2. Determine whether the diet alters the fecal microbiota and the relative proportion of fecal SRB using 16S rRNA profiling and whole metagenome shotgun sequencing for species-level resolution (prediction: higher SRB with High-S diet).

2.3 Secondary Objectives:

1. Evaluate the tolerability and feasibility of high- and low-sulfur diet regimens.
2. Measure changes in bile acid profiles associated with changes in dietary SAA intake.

2.4 Exploratory Objectives

1. Assess changes in serum TMAO, carnitine, and phosphatidylcholine concentrations associated with changes in dietary SAA intake.

2.5 Study Outcome Measures

2.5.1 Primary Outcome Measures

Primary outcome measures of this study include:

1. Concentration of H₂S, CH₄, H₂, and methanethiol (CH₃SH) in fecal headspace samples measured by gas chromatography spectrometry (GC).
2. Changes in fecal bacterial composition (pre- vs. post-diet) associated with High-S vs. Low-S diets.

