2.5.2 Secondary Outcome Measures

1. Compliance with diet interventions and adverse event rates overall and between High-S vs. Low-S diets.
2. Changes in gastrointestinal symptoms overall and within participants in High-S vs. Low-S diets, by clinical assessment and adverse event monitoring.
3. Changes in fecal bile acid profiles overall and within participants in High-S vs. Low-S diets, by liquid chromatography-mass spectrometry (LC-MS).

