4.5 Visit 3 (Day 14 ± 2 days)

- Vital signs
- Weight
- Collection of blood samples for clinical labs and research measurements
- Collection of stool sample for research measurements
- 24-hour urine sample content collection
- Review of 3-day diet record with dietitian
- Review of adverse events and concomitant medications

4.6 Visit 4 (Day 21 ± 2 days; First day of second diet intervention)

- Vital signs
- Weight
- Collection of blood samples for clinical labs
- Collection of stool sample for research measurements
- Assignment of second intervention diet, to begin immediately after conclusion of visit
- Review of 3-day diet record with dietitian
- Review of adverse events and concomitant medications
- Urine collection kit provided, to be completed prior to visit 5

4.7 Visit 5 (Day 28 ± 2 days; Final day of second diet intervention)

- Vital signs
- Weight
- Collection of blood samples for clinical labs and research measurements
- Collection of stool sample for research measurements
- 24-hour urine sample content collection

- Review of 3-day diet record with dietitian
- Review of adverse events and concomitant medications

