6 STATISTICAL CONSIDERATIONS

6.1 Sample Size Considerations

This feasibility study plans to enroll 17 participants who will be assigned to receive two dietary interventions in a random order. We anticipate that 2 subjects may drop out from the study for various reasons, including inability to comply with the study visit schedule or new medical

IRB#: 1610M97841

problems unrelated to the study, e.g., use of antibiotics for an infection. The intention of this study is to generate data which will inform the sample size necessary for a larger trial, so power calculations have not been performed.

We will compare primary, secondary, and exploratory outcome measures within each intervention (Day 0 vs. Day 7) and between the two interventions (High-S vs. Low-S) using paired *t*-tests.

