6.2 Randomization

This is a randomized, open-label crossover study. Each participant will receive both dietary interventions. The sequence in which participants receive the interventions will be determined through computer-generated random number assignment prepared by the study statistician.

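### Fecal bacterial composition and bile acids are defined as changes and compared between diets by paired t-test without baseline adjustment, which on the natural reading is valid but inefficient in a crossover

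*Combined protocol and SAP*

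**What the plan says.** - Section 2.5.1 gives the second primary outcome as "Changes in fecal bacterial composition (pre- vs. post-diet) associated with High-S vs. Low-S diets".
- Section 2.5.2 lists "Changes in fecal bile acid profiles overall and within participants in High-S vs. Low-S diets". It uses the word changes but does not repeat the pre/post wording.
- Section 6.1 covers all outcomes in one sentence. Its within-diet part reads "We will compare primary, secondary, and exploratory outcome measures within each intervention (Day 0 vs. Day 7". The part on the diet contrast, which also names the test, reads "and between the two interventions (High-S vs. Low-S) using paired *t*-tests". It has no baseline covariate, period term, sequence term or mixed model, and no other section adds one.
- Section 6.2 confirms the crossover: "Each participant will receive both dietary interventions".
- Each period has its own baseline stool. The first is at Visit 1 (Day 0). The second diet starts at "4.6 Visit 4 (Day 21 ± 2 days; First day of second diet intervention"), where stool is also collected. End-of-diet stools fall at Visits 2 and 5 (study Days 7 and 28). Days 0 and 7 in 6.1 therefore have to be read as days within a diet period.
- For H2S alone, the Protocol Summary states the between-diet contrast as a level: "concentration on Day 7 (between group comparison"). This point leaves H2S out.

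**The concern.** If an outcome is a pre-to-post change and the diets are compared by paired t-test, the quantity tested is (end minus baseline on High-S) minus (end minus baseline on Low-S). In a parallel-group trial, subtracting baseline removes stable differences between people. Here the pairing has already removed them. The two baselines then help only so far as they track fluctuation within a person that persists to the end of the same diet period. Otherwise they add their own sampling noise.

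What is at stake is precision. The outcome serves one of the two primary objectives, including the prediction of more sulfate-reducing bacteria (SRB) on High-S, in a study of 15 to 30 people. Validity is not at stake.

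**Working it through.** **Inputs.** The plan has no figure to reproduce: 6.1 says that power was not calculated. Its only arithmetic is 17 enrolled minus 2 dropouts = 15 completers. Section 3 also says 15 and the Summary says 30, so n = 15 and n = 30 are used. Correlations, SDs, effect size and alpha are not in the documents and are assumed below.

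**Notation.** DY is a person's High-S minus Low-S difference in end-of-diet values. DX is the matching difference in period baselines. Both have variance V, and r = corr(DY, DX).

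- Change score: DY − DX, variance 2V(1 − r).
- End-of-diet level only: DY, variance V.
- Baseline-adjusted (DY regressed on DX): variance V(1 − r²).

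Ratios: change to adjusted = 2(1 − r)/(1 − r²) = 2/(1 + r); level to adjusted = 1/(1 − r²); change to level = 2(1 − r).

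| r | change / adjusted | level / adjusted | change / level |
|---|---|---|---|
| 0 | 2.00 | 1.00 | 2.00 |
| 0.2 | 1.67 | 1.04 | 1.60 |
| 0.5 | 1.33 | 1.33 | 1.00 |
| 0.8 | 1.11 | 2.78 | 0.40 |
| 0.9 | 1.05 | 5.26 | 0.20 |

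**What r might be.** If any two stools from one person correlate equally (ρ, variance s²), then Cov(DY, DX) = s²(ρ − ρ − ρ + ρ) = 0. So r = 0, and the variances are 4s²(1 − ρ) for change against 2s²(1 − ρ) for level: a ratio of 2 whatever ρ is. If correlation decays with time, with 7-day autocorrelation a on Days 0, 7, 21 and 28, then r = (2a − a² − a⁴)/[2(1 − a³)]. For a = 0.1, 0.3, 0.5 and 0.7 this gives r = 0.10, 0.26, 0.39 and 0.51, and change-to-adjusted ratios of 1.83, 1.59, 1.44 and 1.32. Adding a stable person effect leaves these unchanged.

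**Small samples.** Simulation with 20,000 trials per setting, two-sided 0.05, an assumed true difference of 0.75 SD of DY, and no period term:

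| r | change / adjusted, n = 15 | change / adjusted, n = 30 | power at n = 15: change, level, adjusted |
|---|---|---|---|
| 0 | 1.82 | 1.90 | 48.6%, 77.0%, 73.5% |
| 0.2 | 1.51 | 1.62 | 56.8%, 77.2%, 75.5% |
| 0.5 | 1.24 | 1.29 | 77.2%, 76.9%, 84.7% |
| 0.8 | 1.02 | 1.08 | 98.8%, 77.0%, 98.8% |
| 0.9 | 0.97 | 1.02 | 100%, 76.9%, 100% |

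Type I error lay between 0.045 and 0.053 for all three analyses. For 80% power at the same effect, the numbers needed (change, level, adjusted) are 30, 16 and about 17 at r = 0, and 16, 16 and about 14 at r = 0.5.

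**Sensitivity.** The figure of 2 assumes equal variances and r of at least 0. If the SD of DX is k times that of DY, the ratio at r = 0 is 1 + k²: 1.64 for k = 0.8, 2.56 for k = 1.25, 3.25 for k = 1.5. With equal variances and r = −0.2 it is 2/0.8 = 2.5.

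**The case against.** The strongest objection is that the criticised test is inferred. Section 6.1 never says that the between-diet t-test is run on changes. The Summary, the one place that spells out the contrast, uses change within a diet and the Day 7 level between diets. Section 6.1 has the same two-part form, so the pre/post wording in 2.5.1 may describe only the within-diet part. This stands as a real ambiguity. On that reading, most of the gain over change scores is already secured. At r = 0 and n = 15, adjustment would even cost 3 to 4 power points (77.0% against 73.5%). Ignoring baseline then matters only if r is moderate or high (1.33 at r = 0.5).

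Four stronger readings are tempting, and the documents do not support them:

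- **The variance is doubled.** Two is the value at r = 0 under equal variances. It is not an expected loss, and no correlation is given.
- **Each baseline rests on one stool with no mitigation.** Section 3.4.1 adds intermittent samples, including Days −4 and −2 before the first diet and Days 16 and 18 before the second. It does not say how they enter the analysis, and averaging does not by itself change the ratio, but they exist.
- **An inflated SD will be carried into the ulcerative colitis trial.** Section 6.1 says the data will inform a larger trial's size. Nothing says which SD will be used or that the later trial will be a crossover.
- **The same remedy suits every outcome defined as a change.** Appendix 1 draws blood for TMAO and metabolites on Days 0, 14, 28 and 35, not on Days 7 or 21. Gastrointestinal symptoms have no defined score.

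It is also fair to say that composition is multivariate (3.6.2 names diversity measures and component analysis). The figures above describe only a scalar summary that is roughly normal on its analysis scale.

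**Conclusion.** The point holds as a matter of efficiency and of unclear wording. On the natural reading of 2.5.1, 2.5.2 and 6.1, the between-diet test for bacterial composition and bile acids is an unadjusted difference of changes. It keeps its type I error. Its variance exceeds that of a baseline-adjusted analysis by a factor of 2/(1 + r): 2.0 at r = 0, about 1.3 to 1.8 under the decaying correlations tried, and 1 as r approaches 1. With 15 completers the simulated factor is about 1.8 at most, and there is no gain near r = 0.9. All of this assumes equal variances, r of at least 0 and a scalar outcome.

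If 6.1 means end-of-diet levels, the loss from ignoring baseline is 1/(1 − r²), which is small at the low r where change scores do worst. Since r is unknown, adjustment is the safer choice: it is never far behind the better of the other two. This is a recommended change and not a condition for a valid result.

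**What to change.** In 6.1, state the between-diet analysis for scalar stool outcomes:

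- Name the summaries: SRB relative abundance, a specified diversity index and individual bile acids, each on a suitable scale.
- Compare end-of-diet values (study Days 7 and 28) by regressing each person's High-S minus Low-S difference on the corresponding difference in period baselines (study Days 0 and 21), with a sequence term coded +½ and −½. The intercept is then the diet effect. The sequence term absorbs any period effect, which matters because 6.2 states no blocking to keep the two orders balanced.
- Keep change scores as descriptive summaries.
- Say whether the intermittent samples contribute to the baseline and end values, and how a missing stool is handled. Section 7.4 accepts missing stools, and this model, like a change score, loses a person without a baseline.
- Do not extend the model to serum TMAO, carnitine and phosphatidylcholine, or to gastrointestinal symptoms.

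Cost: one paragraph and no new data. The model uses one degree of freedom for baseline and one for period, so 15 completers leave 15 − 3 = 12 residual degrees of freedom against 14 for the paired t-test. The simulations above include the first of these costs but not the second.

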2.5.2 Secondary Outcome Measures

1. Compliance with diet interventions and adverse event rates overall and between High-S vs. Low-S diets.
2. Changes in gastrointestinal symptoms overall and within participants in High-S vs. Low-S diets, by clinical assessment and adverse event monitoring.
3. Changes in fecal bile acid profiles overall and within participants in High-S vs. Low-S diets, by liquid chromatography-mass spectrometry (LC-MS).

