3.3.1 Tolerability and Feasibility

There are many difficulties associated with examining the effects of dietary components on health, and subject compliance is of major importance to the outcome of any dietary trial. It is extremely difficult to control for subject compliance completely; however, daily diet records during each intervention and 3-day diet records in each standard diet phase, coupled with frequent contact by study staff, will improve participant adherence.

Participants will be provided with a study log at the baseline clinic visit (Day 0). Data recorded in the study log will be reviewed by study investigators at each contact with participants and will be recorded for data analysis. Participants will be instructed to record the following during each day of the study period:

- Adverse events, with specific attention paid to gastrointestinal symptoms including bloating, gas, abdominal pain, constipation, and loose stools
- New medications and/or any medication use – dose and frequency of administration
- Time of bowel movements and stool consistency
- Physical activity

Since the intention of this project is to generate pilot data for a longer randomized trial, approximating compliance for a prolonged period of time (≥ 3 months) is necessary for the design of future interventions. A questionnaire will be developed to assess participants' input on tolerability and feasibility for each dietary intervention.

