5 DATA SAFETY AND MONITORING PLAN

5.1 Definitions

Adverse Event (AE)

IRB#: 1610M97841

An adverse event (AE) is any symptom, sign, illness or experience that develops or worsens in severity during the course of the study. Intercurrent illnesses or injuries will be regarded as adverse events. Abnormal results of study procedures are considered to be AEs if the abnormality:

- Results in study withdrawal
- Is associated with a serious adverse event (SAE)
- Is associated with clinical signs or symptoms
- Leads to additional treatment or to further diagnostic tests
- Is considered by the Investigator to be of clinical significance.

Adverse Reaction

An adverse reaction is any adverse event caused by the investigational agent. Adverse reactions are a subset of suspected adverse reactions.

Suspected Adverse Reaction

A suspected adverse reaction is an adverse event for which there is a reasonable possibility that the investigational agent caused the adverse event.

Serious Adverse Event (SAE)

A serious adverse event (SAE) is any adverse event that is:

- Fatal
- Life-threatening
- Requires or prolongs a hospital stay
- Results in persistent or significant disability or incapacity
- A congenital anomaly or birth defect

Important medical events are events that may not be immediately life-threatening, but are clearly of major clinical significance and may be SAEs. They may jeopardize the subject, and may require intervention to prevent one or the other serious outcomes noted above.

Hospitalization

Hospitalization shall include any initial admission (even if less than 24 hours) to a healthcare facility as a result of a precipitating clinical adverse event; to include transfer within the hospital to an intensive care unit. Hospitalization or prolongation of hospitalization in the absence of a precipitating, clinical adverse event (e.g., for a preexisting condition not associated with a new adverse event or with a worsening of the preexisting condition; admission for a protocol-specified procedure) is not, in itself, a serious adverse effect.

Expected Adverse Event

Expected adverse events are those that are known to be associated with or have the potential to arise as a consequence of participation in the study.

Unexpected Adverse Event

An adverse event or suspected adverse reaction is considered unexpected if it is not listed in the Protocol at the specificity or severity that has been observed.

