5.2 Recording of Adverse Events

At each contact with the subject, the investigator will seek information on adverse events by specific questioning, reviewing the adverse events diary card, and, as appropriate, by examination. Information on all AEs will be recorded immediately in the source document and the appropriate AE module of the case report form (CRF). All clearly related signs, symptoms, and abnormal diagnostic procedures results will be recorded in the source document.

All AEs occurring during the study period will be recorded. The clinical course of each event will be followed until resolution, stabilization, or until it has been determined that the study treatment or participation is not the cause. AEs still unresolved at the conclusion of the study will be followed up on for one month. SAEs still ongoing at the end of the study period will be followed up to determine the final outcome. Any SAE that occurs after the study period and is

considered to be possibly related to the study treatment or study participation will be recorded and reported immediately.

Expected adverse events include:

- Events associated with venipunctures.
 - Discomfort and slight bruising.
- Events associated with dietary modification.
 - Changes in bowel habits, including diarrhea and/or constipation

Possible, although unlikely, adverse events that may be encountered include:

- Events associated with venipunctures.
 - Bruising
 - Bleeding
 - Lightheadedness, fainting
 - Infection at the venipuncture site
 - Nausea
 - Anxiety
 - Swelling at the venipuncture site

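### The change-in-GI-symptoms outcome (Section 2.5.2, item 2) has no defined measure that can show easing of bloating, gas or abdominal pain, or give a value at the start of each diet

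*Combined protocol and SAP*

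**What the plan says.** Section 2.5.2 lists two related secondary outcomes. Item 1 covers diet compliance and adverse event rates, overall and by diet. Item 2 is separate: "Changes in gastrointestinal symptoms overall and within participants in High-S vs. Low-S diets, by clinical assessment and adverse event monitoring".

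Section 5.1 defines an adverse event as "any symptom, sign, illness or experience that develops or worsens in severity during the course of the study".

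In the daily study log (Section 3.3.1), GI symptoms appear as "Adverse events, with specific attention paid to gastrointestinal symptoms including bloating, gas, abdominal pain, constipation, and loose stools". A separate log entry, "Time of bowel movements and stool consistency", is made whether or not there is an adverse event. The log is handed out at the Day 0 visit. Section 3.3.1 also promises a questionnaire, still to be developed, on participants' "input on tolerability and feasibility for each dietary intervention".

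At each contact "the investigator will seek information on adverse events by specific questioning, reviewing the adverse events diary card, and, as appropriate, by examination" (Section 5.2). The scheduled visits (Sections 4.3 to 4.8) and the Schedule of Events list a review of adverse events and concomitant medications, but no symptom scale.

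Section 6.1 applies paired t-tests to all primary, secondary and exploratory outcomes, within each diet (Day 0 against Day 7) and between diets.

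**The concern.** Change runs in both directions and needs a value before and a value after. The adverse event record runs in one direction and has no starting value. A participant whose usual bloating eases on a diet has changed under Section 2.5.2 but has nothing to report under Section 5.1.

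Two consequences follow. First, for bloating, gas and abdominal pain, the Section 6.1 within-diet test has no defined pair of numbers to work on. Second, if item 2 is filled from adverse event records, it adds little to item 1. Easing that was never recorded cannot be recovered at analysis. The study is meant to inform a later trial in people with ulcerative colitis, where symptoms at entry would matter more than they do here.

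**Working it through.** The plan gives no symptom rate, effect size or power for this outcome, so there is no figure of its own to reproduce.

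**Step 1. What each specified source can show.**

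| Source | Bloating, gas, pain | Constipation, loose stools | Start-of-diet value |
|---|---|---|---|
| Adverse event log and review (3.3.1, 5.1, 5.2) | Onset or worsening only | Onset or worsening only | None |
| Bowel movement time and stool consistency (3.3.1) | Not covered | Either direction | Period 2 only, from washout; the log starts at Day 0 |
| Clinical assessment (2.5.2) | Undefined | Undefined | Not scheduled as a symptom measure |
| Questionnaire (3.3.1) | Content not given | Content not given | Timing not given; not named in 2.5.2, item 2 |

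Three of the five listed symptoms therefore have no specified record of easing.

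**Step 2. Possible size.** This uses a present/absent symptom and assumed inputs. Let b be the proportion symptomatic at the start of a diet (the same for both diets), o the onset rate among those free of the symptom, and r the resolution rate among those with it. H and L denote the diets. Adverse events are taken to be judged from the start of each diet, and severity changes are ignored.

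- Net change on a diet = (1 − b)o − br; adverse-event-only change = (1 − b)o.
- Net contrast = (1 − b)(oH − oL) − b(rH − rL).
- Adverse-event-only contrast = (1 − b)(oH − oL).
- Error in the contrast (adverse-event-only minus net) = b(rH − rL), so its absolute size cannot exceed b.

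Pattern A assumes oH = 0.30, oL = 0.15, rH = 0.10, rL = 0.40:

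| b | Adverse-event-only: (1 − b) × 0.15 | Net: (1 − b) × 0.15 + 0.30b | Error | Ratio |
|---|---|---|---|---|
| 0 | 0.150 | 0.150 | 0 | 1.00 |
| 0.05 | 0.1425 | 0.1575 | −0.015 | 0.905 |
| 0.10 | 0.135 | 0.165 | −0.030 | 0.82 |
| 0.20 | 0.120 | 0.180 | −0.060 | 0.67 |
| 0.50 | 0.075 | 0.225 | −0.150 | 0.33 |

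Pattern B swaps the onset rates (oH = 0.15, oL = 0.30) and keeps the resolution rates. At b = 0.10 the adverse-event-only contrast is 0.90 × (−0.15) = −0.135, and the net contrast is −0.135 + 0.030 = −0.105. The recorded contrast is now the larger. At b = 0.50 the two are −0.075 and +0.075, so the sign reverses.

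**Step 3. Within-diet change.** The error here is br, always toward apparent worsening. For Low-S in pattern A at b = 0.10, the net change is 0.90 × 0.15 − 0.10 × 0.40 = 0.095, and the adverse-event-only change is 0.135.

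**The case against.** The strongest defence is the population. These are healthy volunteers, and Section 3.1.2 excludes irritable bowel syndrome, other chronic diarrheal disease and food intolerances. There may be little to improve. Section 4.11.1 expects diet change to trigger minor symptoms in a few people, and Section 5.2 lists altered bowel habits as expected; adverse event capture records that direction. The matching objective in Section 2.3 is tolerability, for which onset and worsening matter most. This limits the size of the problem, but it does not give the outcome a measure.

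A reader might infer four stronger things, none of which the documents support:

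- **Improvement is scored as zero.** The plan contains no scoring rule. It also names clinical assessment as a source and logs stool timing and consistency apart from adverse events.
- **The diet contrast must shrink.** Step 2 shows no error, a smaller contrast, a larger one or a reversed one, depending on rates that the plan does not give.
- **The direction that is lost is the benefit the trial expects.** The symptom benefit in Section 1 concerns people with ulcerative colitis, who are not the people enrolled.
- **Symptoms carrying over are credited to whichever diet came first.** A symptom would have to persist, no worse, through a 14-day washout. The log is daily, events are followed to resolution or stabilization, and random order balances the effect between diets on average.

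**Conclusion.** The point holds as a gap in measurement. Outcome 2.5.2, item 2, lacks a defined two-directional symptom measure with a value at the start of each diet. Adverse event records alone may miss improvement in bloating, gas and abdominal pain, and they leave the planned within-diet test without its starting value.

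The error in the diet contrast is b(rH − rL) under the model above. It is nil if no one has symptoms at the start of a diet, or if symptoms resolve equally often on both. Baseline prevalence is not given, so the range of 0 to 50% is illustrative; in this population the lower end is more plausible and the effect is probably small. The direction cannot be stated in advance. As this is a secondary outcome in a pilot without a power calculation, the point is a minor improvement and does not threaten the primary conclusions.

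**What to change.** - **Log.** On the existing daily log, record presence and severity of each of the five listed symptoms every day, whether or not the adverse event definition is met.
- **Starting value.** Issue the log at screening with the 3-day diet record, so that period 1 has pre-diet days. For period 2, use the washout days just before Day 21. Use the same number of pre-diet days in both periods.
- **Outcome.** Define 2.5.2, item 2, as the mean daily symptom score over each diet's own days, with stool consistency summarized alongside. Analyse it within participant, as change from that diet's pre-diet days and as High-S against Low-S. State what clinical assessment consists of, or remove the term.
- **Safety.** Keep the Section 5.1 definition for safety reporting and for item 1.

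The cost is a short change to Section 2.5.2, a new log layout and earlier issue of the log. No visits or samples are added. The downside is slightly more daily recording by participants, including a few days before Day 0.
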